3.5.3 Subject Recruitment

Phase 1: We will recruit 10 AYA survivors of childhood cancers and 10 caregivers through the Rutgers Cancer Institute Long-Term Information Treatment-Effects Evaluation (LITE) program. Invitational letters from [name], the Director of the LITE program, will be sent to patients on the CINJ LITE mailing list. Flyers will be posted and handed out in clinic. Potentially eligible participants will be approached at routine LITE clinic visits to describe the study, answer any questions, and assess interest in participating. If a parent does not accompany an AYA survivor to the LITE visit, we will ask interested AYA survivors to share a flyer with their parent(s). AYAs and parents do not have to be dyads to enroll in the study. We will also recruit 4-8 healthcare providers (e.g., physicians, nurse practitioners, social workers, psychologists) who regularly work with AYA pediatric cancer survivors. These providers will be recruited through the Rutgers Cancer Institute of New Jersey as well as through the AYA and Survivorship Working Groups of the Children's Oncology Group because they will have greater expertise and experience with AYA survivors than community providers.

Phase 2: Peer mentors will be recruited via advertisements in the CINJ LITE clinic and newsletter, AYA cancer support groups, and online forums/social media, such as stupidcancer.org. Following the Children's Oncology Group's approach to recruiting patient advocates, potential mentors will complete an application including two letters of recommendation. The PI or study staff will interview candidates to evaluate interpersonal skills, level of commitment to the program, and counseling or related experience. Participants for the randomized trial will be recruited using the New Jersey State Cancer Registry (NJSCR). All participant information and surveillance data from the NJSCR is collected and maintained by the NJSCR following Standard Operating Procedures (see IRB#Pro20140000992 NJSCR SEER Data Repository). Patient contact procedures, tracking, and data release also follows NJSCR Standard Operating Procedures. Per Standard Operating Procedures, NJSCR staff will contact the physician of record for eligible cases to notify the physician about the study and that staff will be contacting the patient. An introductory letter and flyer will be mailed to potential participants. NJSCR staff will make follow-up phone calls to provide additional information and, for patients who express interest in participating, to obtain permission

Promoting Follow-Up Care Self-Management for Adolescent and Young Adult (AYA) Childhood Cancer Survivors

[name], MPH

to send their contact information to [name] study staff, who will then contact the patient for further details and discussion of consent.

3.5.4 Consent Procedures

The study will be explained to the potential participant by the Principal Investigator or trained study staff via phone. The PI or study staff will review essential elements of consent and answer any questions. Interested and eligible participants will be emailed a link to an online consent form prior to starting the program. To consent, potential participants will be instructed to click "submit the form" button in order to consent.

3.5.5 Subject Costs and Compensation

Phase 1: Participants who drive to the Rutgers Cancer Institute of New Jersey to complete an interview will incur parking costs. Participants will be given \$25 for completion of an interview.

Phase 2: Peer mentors will be asked to travel to the Rutgers Cancer Institute of New Jersey for training; they will be compensated \$100 for their time and travel. Peer mentors and participants will be asked to use their personal phone for communication via phone and text, which may incur costs depending on the participants' phone plan. Peer mentors will be compensated \$100 per participant mentored to cover costs and effort. Participants will receive \$25 per assessment completed (for a total of \$50).

4. Study Variables

4.1 Independent Variables or Interventions

Phase 1: Semi-structured interview guides will be used to conduct interviews. The goal of the interviews is to understand patient, parent, and provider perspectives on the challenges faced by AYAs in managing their health care and on how PSST materials can be adapted to address the challenges of self-management of care.

Phase 2: Independent variables include demographics (age, gender, socioeconomic status, education, employment status, living at home or independently) and cancer diagnosis and treatment history (i.e., diagnosis, time since treatment completion, types of treatment received). Diagnosis and date of diagnosis will be obtained from NJSCR records and the remaining information from self-report.

Peer Mentoring Intervention. Based on initial interviews and feedback on the PSST intervention, we identified five major themes to be addressed in our program. The intervention will include two components: (1) online self-management educational modules using the Rutgers Canvas online course platform and (2) weekly video-conference calls on Doxy.me between the peer mentor and participant. Table 1 shows the content of the five online modules based on preliminary work. Participants are expected to complete one module per week in addition to a call with their mentors. Each module takes approximately 30 minutes to complete and ends with a personalized assignment for the participant to complete on his/her own (e.g., obtain survivorship care plan, make an appointment, practice communication skills).

Participants will be matched with a peer mentor of the same sex and cancer type to the extent possible.^{24,25} The objectives of the first mentor call are to build rapport, exchange stories regarding current long-term follow-up care, and identify the participant's self-management

Promoting Follow-Up Care Self-Management for Adolescent and Young Adult (AYA) Childhood Cancer Survivors

[name], MPH

strengths, weaknesses, and goals. During this call, the mentor will explain that the mentee is expected to complete one online module per week prior to their next scheduled mentor call (one a week for six weeks). The dose was chosen based on other peer mentoring programs that employed weekly Skype calls.^{24,25} Weekly video-conference calls will be made on HIPAA compliant Doxy.me (<https://doxy.me/>) that implements security and encryption protocols to assure that data integrity and privacy is maintained. In addition to weekly calls, the mentor will encourage the participant to work through the assignment and modules via a weekly text message (using TigerText,²⁶ a HIPAA-compliant program) to offer encouragement, support, and relevant resources. Mentor-mentee calls will be recorded and text messages will be archived for supervision and content analysis.

Given that AYAs are high consumers of technology²¹ and tend to have many different educational, work, and social scheduling demands, we believe using online educational modules and technology to connect the peer mentor and participants will be the most efficient delivery system for this group. To capitalize on AYAs’ regular use of technology, peers will provide support and facilitate completion of educational modules via 6 weekly phone calls and secure text messaging. We will utilize the TigerText service that will allow for secure messaging between participants and peer mentors, as well as between the study personnel, peer mentors, and participants.

Table 1. Content of self-management modules

Module	Proposed Content	Transition Readiness Construct
1	
Understanding Treatment History and Survivorship Care Plan
 
 • Name diagnosis, treatments received, risks for late health effects • Obtain (if needed) and store Survivorship Care Plan • Identify necessary health screenings and frequency 	
Knowledge Goals/motivation

2	
Managing Your Health Care
 
 • Review self-management tasks (e.g., make appointments, obtain screenings) • Establish and maintain relationship with primary care doctor • Logistics of insurance and healthcare tasks • Identify barriers to obtaining care and problem solve • Review motivation and confidence to assume responsibility for care 	
Self-Management Skills Self-efficacy Relationships/communication Goals/motivation

3	
Negotiating Family Involvement in Your Care
 
 • Discuss challenges of parents who do not relinquish control & communication skills • Discuss supportive ways to include family 	
Relationships/communication

4	
Dealing with Emotions about Your Health and Follow-Up Care
 
 • Coping with uncertainty of future health • Communicating with providers & families about adult-oriented healthcare 	
Self-Management Skills Relationships/communication

5	
Staying Healthy in the Context of Life Transitions
 
 • Recognize that health must be maintained in the context of other important life transitions (e.g., education, career, relationships) • Skills & resources for healthy diet, exercise, sexual health/fertility, education, career • Identify value in prioritizing health 	
Goals/motivation Self-Management Skills Self-efficacy

Peer Mentor Training. Peer mentors will attend a one-day training workshop conducted by the PI and study staff (similar to other peer mentor programs^{24,27}). Peer mentors will be given the Peer Mentor Handbook, a manual adapted from the National Mentoring Research Center, which details their roles, responsibilities, and an outline for each mentor call. Presentations, interactive discussions, and role plays will be used to teach mentors how to facilitate their mentee’s use of

Promoting Follow-Up Care Self-Management for Adolescent and Young Adult (AYA) Childhood Cancer Survivors

[name], MPH

the online self-management modules, and how to provide informational and emotional support to their mentees. Ethical issues, including confidentiality and setting boundaries with peers, will be discussed. Peer mentors will also be instructed in how to securely transfer audio recordings of their calls with mentees and destroy the original file from their devices. In addition to the in-person training, we will email these instructions. Peer mentors will have regular weekly phone supervision with the PI or trained study staff once assigned mentees to review mentoring calls and discuss any challenges experienced. During this supervision call, the PI or research staff will verbally confirm that peer mentors have destroyed any transferred audio recordings for the study.

4.1.1 Drug or Device Interventions

N/A

4.2 Dependent Variables or Outcome Measures

Phase 1: The primary outcome measure is qualitative interview data. Interviews will be transcribed for analysis (see Data Handling and Statistical Analysis section for details). Participants will also be asked to complete the questionnaires selected for Phase 2 and provide feedback to the study staff regarding how well the questionnaires capture self-management of survivorship care.

Phase 2: The following standardized measures will be administered at baseline and immediately post-intervention (~6 weeks), except where noted:

Transition readiness. The Readiness for Transition Questionnaire – Survivor Version (RTQ)²³ is a 22-item scale evaluating transition readiness for cancer survivors. Respondents are asked to rate the degree to which they are responsible for various aspects of their health care, such as knowing their survivorship care plan, scheduling visits, and filling prescriptions. They are separately asked to rate the degree to which their parents are responsible for managing the same aspects of their care. Two questions ask about the survivors' overall perception of their readiness to transfer to an adult-approach to health care. The RTQ has demonstrated adequate reliability.²³

The Transition Readiness Inventory (TRI), developed using the SMART framework,²⁸ is a comprehensive measure of multiple components of transition readiness. While the RTQ focuses on responsibility for behaviors, the TRI focuses on behaviors *and knowledge, attitudes, and beliefs*. Specifically, the TRI yields a total score and provides scales for the following targets of our intervention: knowledge, self-management skills, self-efficacy for managing care, goals/motivation, and communication with family and providers around survivorship care. The TRI has shown adequate reliability and content validity,^{28,29} and evidence of predictive validity of engagement in adult healthcare.²⁹ We will utilize the total TRI score.

Anxiety. PROMIS Depression and PROMIS Anxiety measures are validated 8-item measures of depressive symptoms and anxiety. We will examine cancer-related anxiety using the Fear of Recurrence Scale,³⁰ which has been used with young adult survivors of childhood cancers.³¹ Finally, we will adapt items to examine anxiety related to healthcare transition and cancer late effects. We will also use the Cancer Related Worry Scale to assess participants' concerns related to their cancer past and future.

Impact of Cancer. Three subscales from the Impact of Cancer – Childhood Cancer Survivors Scale³² will evaluate perceptions of impact on body and health, memory and thinking, and personal growth. Participants will be asked to complete all three subscales; mentors will be

Promoting Follow-Up Care Self-Management for Adolescent and Young Adult (AYA) Childhood Cancer Survivors

[name], MPH

asked to complete body and health and personal growth only to evaluate if mentoring has positive effects on these outcomes.

Perseverance. The Short GRIT Scale³³ is an 8-item measure of perseverance for long-term goals. We will examine the total score as a correlate of transition readiness and adherence to follow-up care.

Barriers to follow-up care & adherence. We will evaluate insurance status, current provider, and other barriers to care with the Follow-Up Care Use and Health Outcomes of Cancer Survivors (FOCUS) measure. Participants will report on appointments, cancer screenings, and other adherence markers.

Treatment Integrity. Peer mentors will record their video/phone conversations with participants for supervision with the PI. Additionally, 10% of tapes will be randomly selected for treatment integrity review using a checklist of the core components of each session.

Mentor/Participant Alliance. A brief measure of personality (Ten Item Personality Inventory³⁴) will be administered to participants and mentors at baseline only to examine whether personality matching relates to perceived relationship alliance. A brief measure of the alliance between the mentor and participant (Working Alliance Inventory – Short Form³⁵) will be completed by mentors and participants at post-intervention only.

Satisfaction with Intervention. At the 6 week post-intervention assessment, participants will be asked to complete a survey regarding their satisfaction with the intervention received and recommendations for improvement. For the intervention group receiving the online modules and peer mentor, items from a standardized set of internet-based intervention evaluation tools will be used - Internet Intervention Utility Questionnaire, Impact Questionnaire, and Adherence Questionnaire.^{36,37} The Utility Questionnaire measures perceived usefulness, enjoyment, and ease of use. The Impact Questionnaire measures perceived effectiveness in improving targeted skills. The Adherence Questionnaire measures barriers to engagement. Objective user data (i.e., log-ins, posts, modules completed) will be obtained unobtrusively from Canvas. Peer mentors will be given an interview (i.e., Peer Mentor Interview) at the end of the program to assess their thoughts about the program (what went well, did not work well, etc.) The participants will also be asked to do a brief (~20 minute) phone exit interview with the PI or the study staff to gather qualitative feedback on how to improve the program in the future (see Participant Exit Interview Guide).

4.3 Risk of Harm

Phase 1: Risks are considered minimal and include breach of confidentiality. Every effort will be made to ensure confidentiality of data.

Phase 2: Risks are considered minimal and include breach of confidentiality. Every effort will be made to ensure confidentiality of data. Peer mentors will be instructed in the importance of maintaining confidentiality and supervised by the PI. Surveys will ask about self-management skills, transition readiness, anxiety, barriers to care, and adherence to follow-up recommendations. Although discomfort related to such questions is unlikely, participants can choose not to answer any question for any reason and may withdraw at any time.

4.4 Potential for Benefit

Phase 1: There is no direct benefit to participants.

Phase 2: There may or may not be a direct benefit to participants. All participants will receive information regarding self-management that may be useful to participants but the study will

Promoting Follow-Up Care Self-Management for Adolescent and Young Adult (AYA) Childhood Cancer Survivors

[name], MPH

evaluate the feasibility of implementing the interventions as well as participant-reported satisfaction and relevant quality of life outcomes.

5. Data Handling and Statistical Analysis

Phase 1 (Aim 1):

Data Management: Digital recordings will be transferred off of the recorders to the PI's secure shared drive as soon as possible following the interview and then erased from the recorder. Transcription will be completed as soon as possible, removing any identifiable information. All transcriptions will be labeled with a subject number rather than any identifiable information. Digital recordings will be deleted after they are described and checked for accuracy. Paper questionnaires will be labeled with an ID number and stored separately from consent forms in a locked cabinet in the PI's locked office. The key linking subject names and subject numbers will be stored electronically on the PI's password-protected CINJ internal shared drive and destroyed at the end of the study.

Data Analysis: Qualitative data will be analyzed using content analysis, following the framework approach described by Pope and colleagues.³⁸ Specifically, themes will be identified based on the a priori theoretical framework (SMART model). Data will be constantly compared to evaluate fit to the model and new themes that emerge from participants' data will be added to the model. An index of themes will be created and applied systematically to the data using NVivo, a qualitative data analysis software. Data analysis will continue until theme saturation occurred (that is, no new themes emerge from additional participants). Participant feedback on questionnaires will be used to determine if any changes are needed to the outcome measures for Phase 2 of the study.

Phase 2 (Aims 2 & 3):

Data Management: The Rutgers Cancer Institute of New Jersey has a contract and Business Associate Agreement with TigerText to supply HIPAA-compliant secure messaging services and archiving of messages. TigerText will be used for secure text messaging with participants and between mentors/mentees. TigerText uses AES-256/SSL encryption and exercises a number of physical, technical, and administrative safeguards to protect all messages and data. At the application layer, TigerText uses Secure Socket Layers (SSL) to encrypt all communication between the web browser and the data center, and a processing pipeline that ensures performance and data privacy between customer accounts. TigerText partners with Sonian to archive the messages between participants, which will be used for supervision of mentors and for content analysis to determine how mentors and mentees communicated during the study. The archived message data will be accessed and downloaded by the PI or project coordinator using the secure TigerText web portal and stored electronically on the PI's password-protected CINJ internal shared drive. These data will be labeled with an ID number rather than participant name or other identifier. All interactions in the TigerText system are included in the audit logs to ensure that administrators are properly using the web portal and its services.

Databases for participant recruitment and tracking and participant survey data will be developed in collaboration with the CINJ Population Science Research Support Core using HIPAA-compliant DatStat software. The Core provides access to the DatStat software, facilitates initial study setup, and assists in the event of any technical problem in using the DatStat software. Approval for use of this software in research studies has been provided by the Rutgers

Promoting Follow-Up Care Self-Management for Adolescent and Young Adult (AYA) Childhood Cancer Survivors

[name], MPH

Biomedical and Health Sciences Institutional Review Board (IRB). (The approval process included: obtaining a Technology Professional Service Agreement and a Business Associate Agreement from DatStat; the approval of a Security Questionnaire from the Rutgers Office of Information Technology; and the completion of a Security Risk and Assessment Tool by the Rutgers CINJ Office of Information Technology.) The software allows for research study personnel to be assigned data access and privileges specific to their role on the study. Study team members are given access to the minimum amount of data needed to perform their role on the study.

Online surveys will be completed by participants using a secure website (hosted on DatStat servers). DatStat secure servers are registered with site certificates provided by AddTrust that provide for advanced encryption over the wire. As each user moves through the survey form, his/her responses are encrypted while in-transit between the browser and DatStat's server using SSL (Secure Sockets Layer) and 40, 56, or 128-bit Public Key Encryption. All servers used for data collection are highly fault-tolerant and equipped with redundant, hot-pluggable power supplies, redundant network interfaces, and RAID 5 hot-swappable disk storage. All primary servers are plugged into a monitored, uninterruptible power supply (UPS). DatStat servers are stored in a locked server cabinet/rack, which are housed in a state-of-the-art, well-ventilated data center. Physical access to servers and data backup is restricted to a minimal number of information technology professionals. The servers are secured with physical and firewall security.

Participants will complete surveys online or via paper (depending on participants' choice). Paper surveys will be identified using only a subject number and will be entered into the database by study staff and kept in a locked filing cabinet accessible only by authorized study staff. We will keep a separate electronic key linking codes and subject names on the PI's department drive. This key will be destroyed at the end of the study. De-identified data will be kept indefinitely. Audio files of video/phone calls between peer mentors and mentees will be recorded using the peer mentor's handheld audio recorder. The peer mentor will then use Rutgers Large File Transfer Service (LiFT) to securely upload the files for the study team to review. This service allows both internal and external users to upload files securely with their email and password. The peer mentors will be instructed to destroy the files after they have successfully uploaded files to Rutgers LiFT for study team to review. Peer mentors will receive training on how to securely transfer the files and delete the files from their devices during the mandatory in-person peer mentor training. The study team will download the files via the secure LiFT service and store them on the Rutgers secure shared drive accessed via a password-protected computer. For participant exit interviews, study staff will record the interview, transfer to the secure shared drive (access limited to pertinent research team members). Recordings will be transcribed as soon as possible, removing any identifying information from the written document. Recordings will be destroyed upon completion of the study procedures.

Data Analysis: We will examine feasibility through study enrollment rates, retention rates, reasons for study drop out, adherence to the intervention, and patient and mentor satisfaction with the program. Descriptive analyses (frequencies, means) will be used to evaluate our hypotheses regarding expected enrollment (>50%), retention (>75%), and completion of intervention sessions (>75%). We based these predictions using the literature describing barriers

Promoting Follow-Up Care Self-Management for Adolescent and Young Adult (AYA) Childhood Cancer Survivors

[name], MPH

to recruiting AYA participants³⁹ and the team's collective experience in intervention development and implementation.

To assess the preliminary outcomes of the peer mentor self-management program, we will evaluate whether participants in the program demonstrate improvement in transition readiness and the impact of cancer, and reductions in symptoms of depression and anxiety. We will also explore adherence outcomes. We will compare scores on outcome measures at the end of 6-week assessment using dependent/paired t-tests. Since the primary purpose of this project is to evaluate feasibility, we recognize that we do not have adequate power to detect small to medium statistical effects. Exit interviews will be reviewed to identify strengths of the intervention, weaknesses of the intervention, and ideas to improve the intervention.

6. Data and Safety Monitoring

This study is minimal risk. The PI and co-investigators will monitor for adverse events and report any events according to RBHS IRB guidelines.

7. Reporting Results

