1.1 Objectives/Hypotheses

Promoting Follow-Up Care Self-Management for Adolescent and Young Adult (AYA) Childhood Cancer Survivors

[name], MPH

Aim 1: Adapt PSST with peer mentoring to improve AYA self-management of long-term follow-up care.

Qualitative research with AYA cancer survivors, parents, and healthcare providers will be conducted to adapt an evidence-based problem-solving skills training (PSST) program to address the needs of AYA survivors.

Aim 2: Evaluate the feasibility of the self-management + peer mentoring program in a pilot RCT.

We will examine feasibility through study enrollment rates, retention rates, adherence to the intervention, reasons for study drop out, and patient and mentor satisfaction with the program.

Hypothesis 1: Based on literature, we expect enrollment >50% of eligible patients and retention >75%.

Hypothesis 2: We expect patients enrolled in the mentor program to complete >75% of intervention sessions

Aim 3: Assess preliminary outcomes of the peer mentoring program.

Hypothesis 3: Participants in the mentor group will demonstrate improvement in self-management skills, transition readiness, and anxiety.

2. Background and Significance

The transition to adult self-management of health care is often ineffectively managed by AYAs.

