3.3 Sample Size Justification

Phase 1: Total sample size is 24-28, including 10 AYA survivors, 10 parents of AYA survivors, and 4-8 physicians who work with AYA survivors. Qualitative data will be analyzed on a continuing basis. Pooling data across participants, we expect 24-28 interviews will be adequate to achieve data saturation (that is, no new themes emerge from additional participants).

Phase 2: 40 AYA survivors and 20 peer mentors will be recruited for the pilot trial to evaluate feasibility (primary objective) and preliminary outcomes (secondary objective). As this is a feasibility study, we recognize we are underpowered to detect small or medium

Promoting Follow-Up Care Self-Management for Adolescent and Young Adult (AYA) Childhood Cancer Survivors

[name], MPH

effects. Published data suggest 5-9% of survivors are African American or Hispanic;²² data from the NJSCR show greater diversity, with 11.6% of patients diagnosed with cancer at age 10-19 during the period of 2008-2012 reporting as African American, 19% reporting as Hispanic, and 5.7% as Asian American/Pacific Islander. We will oversample these groups.

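### The three numeric feasibility hypotheses are judged on point estimates alone, although with 40 participants retention of 31 to 35 is above 75% while its two-sided 95% interval still includes 75%

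*Combined protocol and SAP*

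**What the plan says.** Section 3.3 of the combined protocol and SAP sets the size of Phase 2 and the rank of its objectives: "40 AYA survivors and 20 peer mentors will be recruited for the pilot trial to evaluate feasibility (primary objective) and preliminary outcomes (secondary objective"). Section 1.1 gives the numeric hypotheses. Hypothesis 1 reads "Based on literature, we expect enrollment >50% of eligible patients and retention >75"%, and Hypothesis 2 reads "We expect patients enrolled in the mentor program to complete >75% of intervention sessions".

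Section 5 (Phase 2, Data Analysis) names the method for all three: "Descriptive analyses (frequencies, means) will be used to evaluate our hypotheses regarding expected enrollment (>50%), retention (>75%), and completion of intervention sessions (>75"%). It describes the figures as predictions drawn from literature on recruiting this age group and from the team's experience. Feasibility is also to be described through reasons for drop-out, adherence and satisfaction, and section 4.2 adds participant and mentor interviews.

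No confidence interval, standard error or precision statement for the three rates appears in the documents. There are two remarks on limited size. Section 3.3 says the study is underpowered for small or medium effects. Section 5, in the paragraph on preliminary outcomes, says "we recognize that we do not have adequate power to detect small to medium statistical effects". Neither says how precisely a rate can be estimated from 40 people.

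**The concern.** The plan undertakes to evaluate three threshold hypotheses for its primary objective, and the only summaries it names are frequencies and means. Read literally, 31 of 40 retained (77.5%) supports the retention hypothesis in the same way as 39 of 40. A frequency does not show whether a true rate at or below the expected value is still compatible with the data.

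What is at stake is the wording of the feasibility conclusion. A report could say that retention above 75% was shown when the data only show that the sample value fell above 75%. Anyone planning a larger trial from that statement would be relying on a rate that is less certain than it looks.

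**Working it through.** **Inputs.** From the documents: 40 survivors (section 3.3); thresholds of >50% enrollment, >75% retention and >75% session completion (sections 1.1 and 5). Assumed, because the documents are silent: a two-sided 95% level; all 40 survivors as the retention denominator, with mentors not counted; 40 enrolled as the enrollment numerator. The number of eligible patients is not given, so a range is shown.

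**The plan's own figure.** The sample size of 40 comes with no error rate, power, effect size or interval width, so there is no derivation to reproduce.

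**Retention: smallest count above the threshold.** 30/40 = 75.0% does not satisfy >75%. 31/40 = 77.5% does.

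**Retention: intervals.** The exact (Clopper-Pearson) limits for x of n are the 0.025 quantile of Beta(x, n − x + 1) and the 0.975 quantile of Beta(x + 1, n − x). The Wilson limits are [p + z²/(2n) ± z√(p(1 − p)/n + z²/(4n²))] / (1 + z²/n), with p = x/n and z = 1.96.

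| Retained | Observed | Exact 95% | Wilson 95% | Includes 75%? |
|---|---|---|---|---|
| 31/40 | 77.5% | 61.5 to 89.2% | 62.5 to 87.7% | yes |
| 32/40 | 80.0% | 64.4 to 90.9% | 65.2 to 89.5% | yes |
| 33/40 | 82.5% | 67.2 to 92.7% | 68.1 to 91.3% | yes |
| 34/40 | 85.0% | 70.2 to 94.3% | 70.9 to 92.9% | yes |
| 35/40 | 87.5% | 73.2 to 95.8% | 73.9 to 94.5% | yes |
| 36/40 | 90.0% | 76.3 to 97.2% | 76.9 to 96.0% | no |

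Wilson for 36/40, written out: (0.9 + 0.0480 ± 1.96 × √(0.00225 + 0.00060)) / 1.0960 = (0.9480 ± 0.1046) / 1.0960, which is 0.769 to 0.960.

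**Sensitivity to the level.** The one-sided 95% exact lower limit is the 0.05 quantile of Beta(x, n − x + 1). It is 72.5% at 34/40 and 75.5% at 35/40, so under that convention the range is 31 to 34. Only the top count depends on the choice.

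**How often the point estimate would mislead.** If X is binomial with n = 40, P(X ≥ 31) is the sum over k = 31 to 40 of C(40, k) pᵏ(1 − p)⁴⁰⁻ᵏ. At p = 0.75, where the hypothesis of more than 75% is false, this is 0.44. At p = 0.70 it is 0.20.

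**Enrollment.** With 40 enrolled, the observed rate exceeds 50% if at most 79 were eligible (40/79 = 50.6%; 40/80 = 50.0%).

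| Eligible | Observed | Exact 95% | Includes 50%? |
|---|---|---|---|
| 63 | 63.5% | 50.4 to 75.3% | no |
| 64 | 62.5% | 49.5 to 74.3% | yes |
| 79 | 50.6% | 39.1 to 62.1% | yes |

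From 64 to 79 eligible, the observed rate is above 50% and the exact interval includes 50%. The Wilson interval moves the boundary by one: its lower limit is 50.3% at 64 eligible and 49.4% at 65.

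**Session completion.** The documents give neither the spread of completion between participants nor the number in the mentor program, so no interval width is calculated.

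**The case against.** The strongest reply is that nothing here is an error. Descriptive evaluation is usual for a pilot of this size, the thresholds are worded as expectations, and feasibility also rests on satisfaction, reasons for drop-out and interviews. Naming frequencies and means does not forbid intervals, and they can be computed from the same data at the reporting stage. All of this stands, and it is why the point is minor. What remains is that the plan names its summaries for the primary objective and commits to no statement of uncertainty for them. A confidence interval is itself descriptive, so asking for one does not turn the pilot into a test.

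Some technical objections also stand. The documents set no confidence level, and because the hypotheses are directional a one-sided limit is defensible, which removes 35/40 from the range. The retention denominator is not defined, so 40 is an assumption. For completion, Hypothesis 2 could mean the average percentage completed or the share of patients above 75%, and the session count is itself unclear, since section 4.1 has five modules and six calls. An interval does not resolve that ambiguity.

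The caveat in section 3.3 follows a sentence naming both objectives, so it could be read as covering feasibility too. But it speaks of detecting effects, not of the precision of a rate.

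A reader might infer that the plan has a go/no-go rule applied to point estimates, or that 40 participants are too few for the purpose. The documents support neither: they contain no decision rule for feasibility, and they set no precision target that 40 fails to meet.

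**Conclusion.** The point holds, at minor severity. With all 40 survivors as the denominator and a two-sided 95% interval, every retention count from 31 to 35 lies above 75% without excluding 75%; with a one-sided 95% exact limit this applies to 31 to 34. With 40 enrolled, the same happens for enrollment from 64 to 79 eligible patients under the exact two-sided interval. For completion the gap in the plan is the same, but its size cannot be derived from the documents.

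The consequence is confined to how strongly the feasibility result is stated. It does not put the design, the sample size or the choice of feasibility measures in doubt.

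**What to change.** In section 5 (Phase 2, Data Analysis), add one or two sentences that:

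- report enrollment and retention each with an exact or Wilson two-sided 95% confidence interval, and state the denominators;
- report the mean percentage of sessions completed among patients enrolled in the mentor program, with a 95% interval calculated across participants, and state what counts as a session;
- word the feasibility conclusion from the interval as well as the point estimate, for instance that observed retention was above 75% but that lower rates are not excluded.

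No pass rule and no larger sample is needed. The cost is the added text and a few lines of analysis on data already collected. The downside is a more cautious feasibility statement with visibly wide intervals.
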